# 4.4.5. Study Medication Early Termination or IVIG Infusion Rate Adjustment

In the event that a subject has a potential side effect of the study drug (such as moderate irritability, erythematous rash, urticaria, respiratory difficulties, hypotension) during IV infusion, the clinical site PI will have the option to slow the IVIG infusion rate or stop the infusion of the study drug. If the study drug is stopped prematurely, the subject will not receive any subsequent doses of IVIG, but will be followed for the 360 day duration of this study. Adjustments can be made in response to an adverse event to slow the IVIG infusion rate in order to administer the entire dose of IVIG. Diphenhydramine, acetaminophen or epinephrine can be given to treat hypersensitivity reactions during IVIG infusions. If a subject suffers a level 3, 4, or 5 toxicity or an SAE with evidence of attribution to the IVIG (see NCI CTEP grading system) either during or after the infusion of IVIG, he/she will not receive any further IVIG infusions but will be followed for the 360 day duration of this study.

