IVIG will be initiated on day 3-5 after HPE surgery (HPE is day 0) at a dose of 1 gm/kg body weight by slow intravenous infusion over at least 4-8 hours, or according to local clinical guidelines for rate and time of infusion. The same dose (1 gm/kg) and duration of infusion will be repeated on day 30 and on day 60 after HPE. Ideally the first dose will be administered on day 3 after HPE, however the first dose may be administered on day 4 or 5 after HPE if there is a clinical situation that precludes start of the study medication on day 3. Dose #1 must be given while the subject is still hospitalized. Dose #2 and #3 may be given as outpatient infusions at the study site if the subject has been discharged from the hospital, as expected. The dose will be based on the weight of the subject on the day of the infusion. If the subject has an intercurrent illness or infection that would preclude giving the 2nd or 3rd IVIG dose at the specified times, the subject will be stabilized or treated for this illness and then the IVIG will be given if the investigator believes it will be tolerated. Since there is a 10 day window for administering doses #2 and #3 of IVIG, we anticipate that all doses will be able to be given during this window. If dose #2 is missed for reasons other than an IVIG related adverse event, dose #3 may still be given. Standard precautions will be taken for administering IVIG, including administering IVIG in a controlled setting by experienced nursing staff, and with the immediate availability of intravenous diphenhydramine, intravenous or subcutaneous epinephrine, and oral or rectal acetaminophen. Local site standard protocol for administration of IVIG will be followed, which may include premedication with acetaminophen or diphenhydramine.

A single dosage level of 1 gm/kg of IVIG was chosen for this study (rather than a range of escalating doses) because 1) this dose is effective and commonly used to treat other autoimmune or immune-mediated diseases in children and adults, 2) this dose can be administered intravenously over 6-8 hours during an outpatient research visit, and 3) this dose is usually not associated with significant side effects in children. To attempt to study several escalating doses in this study would imply that there was a therapeutic target for serum IgG that we would be trying to achieve and that the proper dose could be determined based on PK/PD studies. However, there is no target serum level of IgG that is

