known to be effective for BA or for other diseases and, thus, PK/PD studies would be difficult to interpret. Therefore, we chose to use a high dose of IVIG that is effective in other immune-mediated diseases in children and adults and that should be well tolerated by the infants and their families.

Route of Administration: Dose #1 of IVIG will be administered through peripheral IV, central venous catheter or PICC line, whichever is in place for clinical indications on days 3-5 following HPE. It is mandatory that dose #1 be administered during the inpatient post-operative period following HPE. It is anticipated that doses #2 and #3 of IVIG will be administered in the outpatient setting, although these doses could be administered in the inpatient setting if the subject had been admitted to hospital for a clinically indicated reason. If no IV is in place at the prescribed time for doses #1, #2, or #3 of IVIG, then a peripheral IV will be started for the study drug administration and removed after administration of the IVIG. If the family does not allow placement of a peripheral IV for a dose of IVIG, then that dose of IVIG will not be given but the subject will remain in the study and follow the rest of the study protocol, including attempts at administering subsequent IVIG doses.

IVIG Infusion	Day of dosing following HPE*	IVIG dose**
#1	Day 3 (up to day 5)	1 gm/kg body weight
#2	Day 30	1 gm/kg body weight
#3	Day 60	1 gm/kg body weight

Table 2. Schedule and dosing of IVIG following HPE in infants with biliary atr	esia.
--	-------

\*See 4.4.4 Dose and Timing

\*\*Initial dose will be based on subject's weight at time of HPE. Subsequent doses will be adjusted based on subject's weight measured at 30 and 60 days after HPE. HPE = hepatic portoenterostomy; IVIG = intravenous immunoglobulin

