## 7.4.1. Elevation in Blood Pressure related to Increased Fluid Volume

Although unlikely, hypertension could develop due to the fluid volume administered with each IVIG infusion in this study (20 ml per kg body weight over 6-8 hours for each infusion). Vital signs will be continually monitored during the IVIG infusions per institutional protocol. If hypertension develops (systolic BP ≥112 mmHg) during an IVIG infusion, the infusion rate will be reduced or stopped and BP will be measured again in 30 minutes. If BP remains elevated, intravenous furosemide (1 mg/kg/dose) will be an option based on the clinical judgment of the treating physician if fluid volume is considered the likely cause of the hypertension. Alternatively, if the patient is asymptomatic, BP can be re-measured for 30 minutes without treatment. Blood pressure will continue to be monitored each 15 minutes until resolution of the hypertension. If the IVIG infusion must be stopped completely, the subject will not receive further doses of IVIG.

Additional treatment options for the hypertension include:

- a. Treatment choices for hypertension with BP ≥112 mmHg without symptoms
  - Hydrochlorothiazide: 2 mg/kg/day given once or twice a day, or
  - Amlodipine: 0.2-0.4 mg/kg/day given once or twice a day, or
  - Captopril: 0.3-1 mg/kg/day given twice a day
  - Other site-specific treatment choice
- b. Treatment choices for hypertension with BP ≥112 mmHg with symptoms
  - Nifedipine 0.25-0.5 mg/kg/ sublingual
  - Labetolol: 1-3 mg/kg/hour IV
  - Other site-specific treatment of choice

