# 7.4.6. Fluid volume overload

Because of the fluid volume administered with each IVIG infusion in this study (20 ml per kg body weight of a 5% Gammunex-C solution over 4-8 hours for each infusion), individuals with expanded fluid volume, or where fluid volume may be a concern, will not be enrolled in this study. On the day of doses #2 and #3, the physical exam must be completed by a physician prior to the infusion to rule out signs of fluid overload or congestive heart failure. IV fluids will be reduced by 20 ml per kg per day for the day that dose #1 is administered, and if IV fluids are being administered for the days that doses #2 and #3 are given. If fluid volume problems develop during an IVIG infusion, the infusion will be stopped and appropriate steps will be taken to reduce fluid intake and consideration of use of intravenous diuretic medications (e.g. furosemide I mg/kg IV). If fluid volume status has improved at the time of the subsequent IVIG dose, the dose may be given.

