# 7.4.8. Hypersensitivity Reactions (Fever, rash, urticaria)

Severe hypersensitivity reactions may rarely occur with IVIG products, manifested by fever, erythematous rash, urticaria, breathing difficulties and hypotension. In case of hypersensitivity, IVIG infusion will be discontinued immediately and appropriate treatment will be initiated. Medications such as epinephrine will be available at time of IVIG infusion for immediate treatment of acute hypersensitivity reactions. Some centers give prophylactic acetaminophen and diphenhydramine prior to IVIG given for clinical indications, to prevent these reactions. This will be allowed as per local protocol if this is the standard of care for IVIG infusions at any study site. Patients with known antibodies to IgA (those with congenital IgA deficiency) may have a greater risk of developing potentially severe hypersensitivity and anaphylactic reactions, however this has not been observed in infants treated for Kawasaki Disease who do not routinely get tested for IgA deficiency. In addition, infants under 4 months of age may normally have unmeasurable IgA, thus determining IgA deficiency at this age may not be possible. IVIG will not be used in subjects who have a history of hypersensitivity reaction to IVIG. If a subject develops a hypersensitivity reaction to the IVIG, no further infusions of IVIG will be given.

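### The protocol gives conflicting rules on IVIG after a fluid-volume stop, on infusion reactions and on the weight for dose 1, and sets no precedence; the first two can change the primary feasibility score.

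*Protocol*

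**What the plan says.** **After a stopped infusion.** Protocol 4.4.5 deals with potential side effects during infusion. There "the clinical site PI will have the option to slow the IVIG infusion rate or stop the infusion of the study drug", and "If the study drug is stopped prematurely, the subject will not receive any subsequent doses of IVIG". Section 7.4.6 covers one such effect: "If fluid volume problems develop during an IVIG infusion, the infusion will be stopped". It then adds: "If fluid volume status has improved at the time of the subsequent IVIG dose, the dose may be given". Section 6.1.5.b lists fluid overload among the reported side effects of IVIG.

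**Infusion reactions.** The examples in 4.4.5 include erythematous rash, urticaria, respiratory difficulties and hypotension. It allows the rate to be slowed so that the whole dose goes in, and allows drugs to treat hypersensitivity while the infusion runs. Section 7.4.8 names largely the same signs and states: "In case of hypersensitivity, IVIG infusion will be discontinued immediately and appropriate treatment will be initiated". It ends by barring any further IVIG after a hypersensitivity reaction.

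**Weight for dose 1.** The text of 4.4.4 states: "The dose will be based on the weight of the subject on the day of the infusion". The Table 2 footnote in the same section sets the initial dose by "weight at time of HPE. Subsequent doses will be adjusted based on" the weights measured at 30 and 60 days. Dose 1 is given on day 3 to 5 after HPE.

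**The outcome affected.** Section 4.3.1 counts an infant as a feasibility success only if 80% or more of every one of the three doses was given at the prescribed times. Section 5.3 reports the percentage with a one-sided 90% Clopper-Pearson lower bound.

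**The concern.** A site that meets fluid overload or an urticarial reaction during an infusion finds two instructions in the same protocol with different consequences for later treatment. Section 1 describes a network of 16 centres, so different readings are a realistic prospect.

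Two things are at stake. The first is consistent safety handling of young infants, including whether they are exposed again after a reaction. The second is the meaning of the first primary outcome: a rule that withholds a later dose makes the infant a feasibility failure, and a rule that permits it leaves success open. The feasibility percentage would then partly reflect which section a site followed.

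**Working it through.** **Plan's own figure.** Section 5.2.1 gives the power for Aim 1 outcomes (null 40% or higher, true 20%, one-sided 10%) as 70% with 23 infants and 79% with 29. Take the largest c with P(X ≤ c | n, 0.40) ≤ 0.10; power is P(X ≤ c | n, 0.20). For n = 23, c = 5 and power is 69.5%. For n = 29, c = 7 and power is 79.0%. Both figures reproduce and are not in dispute.

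**Fluid-volume stop.** Both 4.4.5 and 7.4.6 apply to the same infant, because fluid overload is a listed IVIG side effect. Suppose the remaining doses, where allowed, are given in full and on time:

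| Stop occurs at | Share of that dose infused | Score under 4.4.5 | Score under 7.4.6 |
|---|---|---|---|
| dose 1 or 2 | under 80% | failure | failure |
| dose 1 or 2 | 80% or more | failure (later dose barred) | success possible |
| dose 3 | any | same under both | same under both |

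Only the second row changes the score.

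**Hypersensitivity reaction.** At dose 1 or 2, a site using 4.4.5 may slow the infusion, treat, complete the dose and give the rest: a success. Under 7.4.8 the later doses are barred: a failure, however much had been infused. At dose 3 no later dose remains to be barred, so the score could differ only if discontinuation came before 80% was in. The two sections agree on later doses if the site chooses to stop under 4.4.5. They also agree if the event is a level 3 to 5 toxicity or an SAE attributed to IVIG, because 4.4.5 then bars further infusions as well.

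**Weight for dose 1.** Let d be the proportional weight change from HPE to the infusion day. At a fixed amount per kilogram:

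- Dose on HPE weight ÷ dose on infusion-day weight = 1/(1 + d). This is below 0.80 only if d > 0.25.
- Dose on infusion-day weight ÷ dose on HPE weight = 1 + d. This is below 0.80 only if d < −0.20.

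For an assumed 5% gain the ratios are 1/1.05 = 0.952 and 1.05. The grams differ by about 5%, and the 80% threshold is not approached.

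**Size per infant whose score changes.** The step is 1/29 = 3.4 points. The one-sided 90% lower bound is the 0.10 quantile of Beta(x, n − x + 1); at x = n = 29 it equals 0.10^(1/29) = 0.924.

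| Successes of 29 | Estimate | Lower bound |
|---|---|---|
| 29 | 100% | 92.4% |
| 28 | 96.6% | 87.2% |
| 27 | 93.1% | 82.7% |
| 26 | 89.7% | 78.4% |

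In this range each changed score lowers the bound by about 4 to 5 points.

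**The case against.** The best defence is that 4.4.5 is the general rule and section 7.4 holds the event-specific rules. Fluid overload is not among the examples in 4.4.5, and both 4.4.4 and 6.1.5.b refer staff to 7.4. This reading is possible, but the protocol never states it. The 4.4.5 examples are illustrative and its bar on later doses is unqualified. Section 4.4.4 also sends readers to Section 6 for rate adjustment and early termination, although the section with that title is 4.4.5. Section 6.1.5.b in turn points to the institutional action plan as well as to 7.4.

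On hypersensitivity, the difference could be one of severity, since 7.4.8 opens with severe reactions. That carries some weight. But its heading and its closing bar are not limited to severe reactions, and 4.4.5 itself names respiratory difficulties and hypotension among the effects for which slowing is an option.

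Three stronger readings are tempting and are not supported:

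- **Section 7.4.1 as a further contradiction.** It says "If the IVIG infusion must be stopped completely, the subject will not receive further doses of IVIG". That agrees with 4.4.5 and concerns hypertension, a different trigger from 7.4.6. Different rules for different events do not by themselves conflict.
- **The weight conflict as a threat to the feasibility score.** It would need a gain above 25% or a loss above 20% within 3 to 5 days.
- **Every infant handled under the other rule as a 3.4-point shift.** The shift arises only in the narrower cases worked out above.

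**Conclusion.** The three inconsistencies are present in the current text, and no order of precedence resolves them. The firm consequence is that infants with the same event may be handled differently across sites, and that dose 1 may be calculated on either of two weights.

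The effect on primary feasibility is real but limited to two situations: a hypersensitivity reaction at dose 1 or 2 that one site would slow and complete and another would discontinue; and a fluid-volume stop at dose 1 or 2 after 80% or more was infused. Each infant so affected moves the estimate by 3.4 points of 29 and the lower bound by about 4 to 5 points near full success.

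This assumes that all 29 infants are in the denominator and that permitted later doses are given in full and on time. The documents give no rates for these events and no figure for perioperative weight change, so the number of infants affected cannot be estimated. The case for correction therefore rests on consistent handling and a clearly scored primary outcome, and no expected bias of known size has been shown.

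**What to change.** The sponsor and clinical leads should reconcile 4.4.5 with 7.4.6 on dosing after a fluid-volume stop, 4.4.5 with 7.4.8 on hypersensitivity reactions, and the text of 4.4.4 with the Table 2 footnote on the weight for dose 1. One rule should stand for each situation, and the protocol should say which section governs where a general and a specific rule overlap. The cross-reference in 4.4.4 to Section 6 should be corrected at the same time. The feasibility definition in 4.3.1 should then state how an infant is scored when the reconciled rule withholds or permits a later dose. Which rule or weight is right is for the clinical leads and is not judged here.

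The cost is one clarifying amendment, best made before enrolment. Sample size, visits and analysis method do not change.

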# 4.6. Other perioperative and medical management

All subjects with BA will undergo standard surgical HPE following the technical guidelines agreed upon by the ChiLDREN Surgical Committee. All subjects will receive antibiotics intravenously for at least 2 days postoperatively or until they are able to tolerate oral/enteric feedings. Intravenous antibiotics are routinely used postoperatively at ChiLDREN centers as prophylaxis against ascending cholangitis and to prevent perioperative wound infections. The choice of antibiotics will be according to the local standard of care. Once oral/enteric feedings are tolerated, oral trimethoprim-sulfamethoxazole (TMP/SMZ, 4-5 mg TMP/kg/day) will be initiated and continued for 180 days after HPE for cholangitis prophylaxis. In the event of an episode of cholangitis despite antimicrobial prophylaxis or following the termination of the prophylaxis, subjects will be treated with parenteral antibiotics according to the standard of care at the clinical center where the subject is enrolled. Thereafter, prophylaxis with oral TMP/SMZ will be used for an additional 180 days from completion of the IV antibiotics, or until 360 days (end of the study). In the unlikely event that the subject develops a hypersensitivity reaction to TMP/SMZ manifested as a skin rash or fevers (see section 7.4.3), the medication will be discontinued promptly. The subject may receive all remaining IVIG infusions and continue with follow-up visits as per protocol.

Other medications and treatments that are part of the routine BA clinical care following HPE will be continued as outlined in Section 4.7.

# 4.7. Routine clinical care guidelines for ChiLDREN

Routine clinical care guidelines were established for infants enrolled in the ChiLDREN prospective database study (PROBE; P003) and will be followed in this clinical trial. These guidelines were developed based on a consensus of the ChiLDREN clinical investigators in regard to optimal medical and nutritional management and the frequency of follow-up visits for infants with biliary atresia.

# 4.7.1. Physical Exam

At each medical encounter/visit, the following will be obtained:

- Height or recumbent length, weight, occipital-frontal head circumference
- Vital signs.
- Skin examination for rash, urticaria, jaundice, xanthomas, palmar erythema, and vascular pattern.
- Abdomen examination to determine liver size and texture, spleen size, presence of ascites.
- Examination of extremities

# 4.7.2. Diet

When the total serum bilirubin is  $\geq 1.5$  mg/dL and the child is less than 12 months of age, MCT-containing formula or breast milk should be used, as long as the child's growth is "adequate". When the total bilirubin is <1.5 mg/dL, the child can be transitioned to standard infant formula (if <12 months of age) and whole milk (if  $\geq$  12 months of age) or breast milk can be continued if the preference of the family. MCT-containing formula or breast milk will

be continued if the total bilirubin is  $\geq 1.5$  mg/dL and the child is 12 months of age or older. When growth is inadequate, measures will be taken for nutritional rehabilitation according to medical management used at each ChiLDREN clinical center. Solid foods will be initiated at the discretion of the subject's primary care provider. MCT-containing formula will not be supplied or paid for by this study, since it is standard of clinical care.

Growth	Age (mo)	Total Bilirubin (mg/dL)	Diet
Adequate	<12	> 1.5	MCT-containing formula or breast milk
Adequate	<12	<1.5	Standard formula or breast milk
Adequate	> 12	> 1.5	MCT-containing formula [or breast milk]
Adequate	> 12	<1.5	Whole milk or breast milk
Inadequate	N/A	N/A	Nutritional rehabilitation

# 4.7.3. Vitamin supplementation

Supplementation with fat-soluble vitamins is part of the standard clinical care of infants with BA. Therefore, it is recommended that all subjects in this study with total bilirubin  $\geq$ 1.5 mg/dL should receive the following:

- a. AquaDEKs® vitamin drops or similar vitamin preparation: 2 ml orally per day
- b. Vitamin K : 2.5 mg orally co-administered with AquaDEKs® vitamin drops on Mondays, Wednesdays and Fridays
- c. Other individual vitamin supplements as needed to maintain normal serum levels of fat-soluble vitamins

AquaDEKs® and Vitamin K may be stopped when the total bilirubin is <1.5 mg/dL (normal total serum bilirubin). Serum vitamin levels and prothrombin time/INR will be measured during follow-up visits after HPE as per normal clinical care at the study sites. When an abnormal vitamin value is obtained, the dosage of the specific vitamin will be augmented or reduced, as appropriate, per the local study site standard of clinical care. Repeat levels will be obtained as per local standard of clinical care. This study will not pay for the vitamin supplements used in this study nor for the serum measurements of fat soluble vitamins.

#### 4.7.4. Ursodeoxycholic acid

• Ursodeoxycholic acid suspension: 20 mg/kg/day divided BID orally until the end of the 360 day post-HPE visit.

This medicine may improve bile flow and is the standard of care for biliary atresia. *This study medication will be provided by the study to the families at no charge.* 

Ursodeoxycholic acid will be discontinued if serum total bilirubin is >15 mg/dL to avoid potential toxicity.

# **4.7.5.** Antibiotics for prophylaxis against ascending cholangitis (see also Section 4.6)

• TMP/SMZ: 4-5 mg TMP/kg/day orally for 180 days following HPE.

This is considered a study medication and will be provided by the study to the families at no charge.

In the unlikely event that the subject develops a hypersensitivity reaction to TMP/SMZ it will be discontinued. The subject will receive all remaining IVIG infusions and continue with follow-up visits as per protocol.

# 4.7.6. Routine childhood immunizations

It is expected that routine primary immunizations will be given to all children by their primary care provider as recommended by the Committee on Infectious Diseases of the American Academy of Pediatrics (AAP). IVIG has been shown to interfere only with live virus vaccines but not killed virus vaccines. Only killed virus vaccines will be administered to infants under one year of age in this trial. Participants may receive live attenuated viral vaccines at 12-15 months of age (MMR and Varicella vaccinations) because it is very unlikely that substantial amounts of IVIG would still be circulating in the participant at that time. This is based on the last IVIG dose being given 60 days after the HPE procedure, the latter which is expected to be performed at 40 to 100 days of age in the majority of participants with the latest it can be performed in this trial being 180 days of age. The Rotavirus vaccines (live attenuated virus vaccines) are not recommended in children with significant abdominal disorders or following abdominal surgery, and therefore are not recommended for study participants.

Development of infectious diseases and vaccine-preventable diseases Subjects will be prospectively monitored for the development of infectious diseases and vaccine-preventable diseases. Parents and primary care providers of all enrolled subjects will be instructed to contact the study coordinator promptly at the time of any infectious acute illness that leads to visit to the primary care provider, to an emergency department, or if the subject requires hospitalization. An Adverse Event Form will be completed within 24 hrs of each report.

